This document describes the statistical analysis plan (SAP) for the PIRATES-COV trial. The SAP was developed according to guidelines found in ICH E9. This SAP contains more technical and detailed elaboration of principal features of the analysis described in the protocol, and includes procedures for executing the statistical analysis of the primary and secondary variables. Planned ancillary studies will not be included in this SAP and will have their own separate SAP. Other unplanned exploratory analyses not identified in the SAP will be clearly identified in the reporting as well as any deviation in the analyses from this original SAP.

The SAP should be executed once the trial database lock (DBL) has been achieved. Analyses will be double-blinded for the randomization group. All the analyses will follow the Statistical Analysis Plan (SAP) described in this document. Analyses will be done under the responsibility of the trial statistician at the Data Coordinating Center (Applied Clinical Research Unit (URCA), CHU-Sainte-Justine, Montreal).

During the analysis processes, the study Principal Investigator, the Executive Committee and the Steering Committee will be kept blind to the randomization group until final disclosure of the study results.

5. Statistical analysis plan revisions

Any changes to the SAP will be logged in the following table:

Protocol version	Updated SAP version	Section number	Description of and reason for change	Date changed

6. Roles and responsibilities

Principal Investigator

[name] PhD, CRC-CHUS et Département de gynécologie/Obstétrique Faculté de médecine et des sciences de la santé (FMSS), Université de Sherbrooke (UdeS)

Research Co-presenters

[name], Centre de recherche sur le vieillissement du CIUSSS de l'Estrie-CHUS, UdeS

[name], CR-CHUS et Immunologie-Biologie cellulaire, FMSS, UdeS

Collaborators

[name], Médecine, FMSS, UdeS

[name], Sciences de la santé communautaire, FMSS, UdeS

[name], Immunologie-Biologie cellulaire, FMSS, UdeS

[name], Microbiologie et immunologie, Faculté de médecine, ULaval

[name], Gynécologie et obstétrique, Faculté de médecine, ULaval

[name], Gériatrie, FMSS, UdeS

[name], Sciences de la santé communautaire, FMSS, UdeS

[name], Biologie, Faculté des sciences, UdeS

[name], Médecine sociale et préventive, École de santé publique, UdeM

Microbiota could partly explain the variations in flu vaccine responses between individuals or populations. Two meta-analyses have studied the effect of probiotics in the context of influenza vaccination. Lei et al. (9 RCTs, N=623) showed a significant improvement in antibody levels for the H1N1 strain (OR=1.83, 95% CI 1.19-2.82), the H3N2 strain (OR=2.85, 95% CI 1.59-5.10), and the B strain (OR=2.11, 95% CI 1.38-3.21). Yeh et al. found similar results with a significant increase in antibody levels (+20% A/H1N1, +19.5% A/H3N2, and +13.6% B). In 2019, an RCT showed an increase in immune response to the flu vaccine in an elderly population. These studies have limitations, often with small sample sizes and significant variability in: i) the probiotic (strain, dose, viability) and ii) mode of administration (e.g., duration). It has also been shown that antibiotics reduce the effects of vaccine boosters in people with low pre-existing antibodies concentrations.

8. Study Objectives

Primary objective:

Reduce the percentage of elderly individuals not presenting RBD antibodies, six months after the booster vaccine dose, through the intake of two strains of probiotics compared to placebo.

Secondary objectives (Obj S):

Obj S1: Compare between study groups the presence of RBD antibodies through a longitudinal analysis at three different time points (baseline, 3 months, and 6 months post-vaccination).

Obj S2: Compare between study groups the presence of anti-N antibodies through a longitudinal analysis at three different time points (baseline, 3 months, and 6 months post-vaccination).

Obj S3: Compare the proportion of the antigens or PCR confirmed cases of COVID-19 with symptoms and the proportion of COVID-19 asymptomatic cases between study groups.

Obj S4: Compare the evolution of antibodies and memory B cells, CD4+ T cells, and CD8+ T cells at baseline and 6 months post-vaccination (between study subgroup of participants).

Section 3: Trial Methods

9. Trial design

Inclusion Criteria:

- Men or women aged between 65 and 89 years
- having received 3 doses of an mRNA vaccine (Pfizer-BioNTech or Moderna), with the last dose being more than five months ago
- willing to receive a booster dose of the vaccine
- having access to a phone or the internet
- capable of providing informed consent
- residing in the province of Québec

Exclusion Criteria:

- patients who had COVID-19 in the last 3 months (clinical and/or serological data retrospectively, subgroup of 100 participants only)
- patients already taking part in another randomized clinical study
- with possibly affected cognitive functions (a score < 9 is needed for inclusion according to the Functional Activities Questionnaire (FAQ))
- consuming probiotics on the day of inclusion
- with allergies (soy, lactose, yeast, maltodextrin)
- consuming antibiotics on the day of inclusion
- with a chronically weakened immune system (AIDS, etc.) or undergoing anti-cancer treatment (chemotherapy or radiotherapy)
- actively being treated for a gastrointestinal condition or disease (gastric ulcers, Crohn's disease, celiac disease, ulcerative colitis, etc.)
- Any other serious condition that, in the judgment of the study physician, would prevent safe participation in the study until the end
- Not speaking either French or English

All subjects in the study are asked to collect a dried blood sample at three different time periods (inclusion, 3 months and 6 months), and a stool sample at the time of inclusion. A subsample of

subjects (n = 100) was selected to undergo additional blood tests at two different time periods (inclusion and 6 months); this subsample is used for the secondary analysis S4.

10. Randomization

Randomization is carried out with a 1:1 ratio, probiotics (intervention) versus placebo after inclusion. Prior to the start of the study, the randomization list will be generated by the statistician considering age and gender stratification. Age stratification will be done in 2 strata: 65-79 years old and 80-89 years old.

Randomization will be done via the REDCap application. The statistician will create different randomization tables according to gender (female/male) and age strata. These tables will then be imported into REDCap for automatic randomization based on the age and gender information of each participant.

During the course of the trial and until the database is locked, study personnel at the site (principal investigator and research team) and at the Sponsor (research specialists and laboratory manager) will not be informed of the group allocation. Based on a blinded randomization method (according to the algorithm built into the REDCap platform), participants will be assigned to one of the 2 groups. The CHUS pharmacy will prepare the products according to the allocation on REDCap.

11. Level of statistical significance

The primary outcome measure is a measure of RBD antibodies. We consider the dichotomous value (detectable or undetectable) for the level of statistical significance. We used an expected proportion of 30% of elderly individuals not presenting RBD antibodies in the placebo group at 6 months. Expecting that the intervention is over-the-counter and inexpensive, we calculated the sample size to detect a relative difference of 33%, with a two-sided alpha of 5% and a power of 80%; 584 participants are required. With a 15% attrition rate at 6 months, the total sample size is 688 patients.

Final analyses will begin in 2025 after database lock.

Unless otherwise specified, the alpha will be set at 0.05 for statistical significance.

12. Adverse events reporting

Taking probiotics has very few undesirable side effects, unless taken in doses higher than the recommended dosage (bloating, intestinal irritation, constipation). Side effects for probiotics (product adherence, medication intake, adverse effects) will be collected once every 2 weeks for 33 days. For the booster vaccine dose, all adverse events, such as local reactions (pain at the injection site or arm, local erythema, lymphadenopathy) and systemic reactions (fever, fatigue, headaches, joint pain, digestive issues, flu-like symptoms...) will be recorded once a week for 2 weeks. If a participant reports symptoms related to an infection, we will ask them to realize a COVID-19 test. If the participant is unable to get tested, we will provide them with a box of rapid tests for self-testing. If a participant needs to be hospitalized, data related to the hospitalization

will be collected. This process will be carried out with the utmost respect for the healthcare teams' work, aiming not to add extra workload. Various data collection methods are possible:

- From the medical records after the end of hospitalization;
- By contacting the patient after discharge by phone or email;
- We will ask the participant at the beginning of the study to inform us of their place of care if they leave their home;
- By contacting the designated reference person identified at the beginning of the study.

The monitoring committee will ensure the safety of the participants and will be notified of any serious adverse events (within 48 hours) and non-serious adverse events (one monthly report).

13. Definition of adherence and how adherence will be presented

Adherence will be estimated via self-reported adherence in the logbooks pre-vaccination and post-vaccination completed online or on paper (according to the preference of the participant). If at least 80% of the doses prescribed was taken both pre and post vaccination (i.e. 12 pills out of 15 for both periods), and if no more than 120% of the total dose prescribed was taken (i.e. no more than 36 pills), we consider that the participant adhered to the protocol.

14. Lost to follow-ups and withdraws

We conservatively anticipated that 15% of participants would be lost to follow-up at 6 months. The observed number of lost subjects was lower, as only 9.8% of subjects were lost at some point during the study.

[figure not shown]
15. Definition of analysis populations e.g. Intention-to-treat, per-protocol

Intent to treat analyses will include all participant randomized to either control or intervention arm including participants lost to follow up.

Per-protocol analyses will include all participant randomized to either control or intervention arm, excluding participants lost to follow up, those with less than 80% adherence for each period (or with more than 120% adherence in total) to the assigned intervention, subjects with 5 months or less between the their last vaccine dose and their scheduled booster dose, subjects who did not get the booster shot as planned, subjects taking probiotic supplements at inclusion, during product intake or more than one week in continuous during the follow up phase subjects with other previous vaccines than Pfizer-BioNTech or Moderna, and subjects taking antibiotics at inclusion or during product intake(antibiotics taken less than 2 hours before the treatment probiotic or placebo).

16. CONSORT Diagram

Per recommendations in the CONSORT guidelines, the statistician will generate a flow chart indicating the number of individuals screened and enrolled, the reasons for ineligibility, the number of individuals randomized, and the number of participants in each group who provided blood samples at each stage of the study.

17. Descriptive analyses and positivity checks

Distribution of sociodemographic and clinical variables measured at inclusion will be described for each group. The proportion of missing data will be described for each variable. Continuous variables will be presented as means and standard deviations or geometric means and 95% confidence intervals (CIs). Categorical variables will be presented as N (%).

The probability of intervention conditional on baseline variables will be calculated for all observations to confirm the effectiveness of randomization and to verify the balance of baseline factors in each intervention arm. Overall probability will be graphed to confirm that there are no violations of positivity. Should there be positivity violations, the statistician will investigate and characterize participants who have a less than 5% or greater than 95% probability of intervention. The statistician will then notify the investigators and discuss whether a restriction of the analysis is necessary.

To assess the quality of participant blinding, participants assessment of their arm will be compared against the true randomization status.

A table describing the demographic and clinical characteristics at baseline randomization will be generated, however statistical testing will not be done comparing individual variables between groups.

Participation in follow-up assessments and completeness of outcome data will be calculated and compared for each time point by study arm. A sensitivity analysis on loss to follow-ups will be performed using weights or extreme case scenarios.

18. Intention to treat

For the primary analyses, we will follow an intention to treat model. All participants will be assigned intervention status based on their randomized assignment. We will use an inverse probability of censoring for missing outcome data. Participants lost to follow-up will be censored.

19. Adherence per protocol analysis

Per-protocol analyses will include all participant randomized to either control or intervention arm, excluding participants lost to follow up or those non-adherent to the assigned intervention. Adherence will be estimated via self-reported adherence in the logbooks pre-vaccination and post-vaccination completed online or on paper (according to the preference of the participant). If at least 80% of the doses prescribed was taken both pre and post vaccination (i.e. 12 pills out of 15 for both periods), and if no more than 120% of the total dose prescribed was taken (i.e. no more than 36 pills), we consider that the participant adhered to the protocol.

20. Outcome definitions

Primary outcome

RBD antibodies: i) can powerfully block the binding between SARS-CoV-2 and its ACE2 receptor, and ii) are a correlate of antibodies and vaccine efficacy. The RBD antibody level will be determined by a validated ELISA test (95% sensitivity and 100% specificity). The primary outcome measure is a dichotomous measure of RBD antibodies (detectable or undetectable). The positivity threshold was defined based on the mean optical density (colorimetric reaction on blotting paper) of negative sera +3 SD. Possibly, a quantitative variable will be available.

Secondary outcomes

The Anti-N antibodies will be determined by the same procedure than for the dichotomous RBD antibody level (90% sensitivity and 95% specificity).

For the comparison of asymptomatic versus symptomatic COVID-19 cases, a subject will be classified as asymptomatic if the anti-N test confirms that the subject had COVID-19, but the subject never reported a positive COVID-19 test during the time period.

For the Ac (OS 4): we will perform a pseudotyped viral neutralization test. The S protein expressed by the vesicular stomatitis virus and HEK293 cells overexpressing ACE2 will be used. Memory B, CD4+ T, and CD8+ T lymphocytes (OS 4) will be studied by flow cytometry. B cells will be identified with appropriate markers and the S protein coupled with a fluorochrome. Memory CD4+ and CD8+ T cells will be identified following activation by the S protein with the appropriate markers.

21. Descriptives analyses of outcome measures

Detectability of Ac RBD will be described and compared between groups using chi-squared or fishers exact tests as appropriate. If quantitative RBD measures are available will be compared by intervention arm using t-test or rank sum testing as appropriate based on the distributions.

Distribution of log of score measures will be calculated for each of: Ac-n and lymphocytes B, T CD4+ et T CD8+ at inclusion and 6 months post vaccine. The distributions will be generated overall and comparatively by intervention arm using t-test or rank sum testing as appropriate based on the distributions.

22. Stratifying variables

The analysis will follow the randomization strategy. Gender and age were used as stratifying variables. We will use the same categories in the analysis.

23. Primary outcome analyses

The primary analysis on the dichotomous criterion (Ac RBD) at three time points (baseline, 3 months, and 6 months post-vaccination) will use a GEE logistic regression model with a logistic link function for longitudinal binary data. This model will also include the stratification variables used for randomization (age group and sex). The other variables included in the model are the group (placebo vs. probiotic) and time (baseline, 3 months, and 6 months post-vaccination). The main parameter of interest in this model will be the interaction between the group and time.

Logistic regressions will also be performed for fixed time strata (3 months and 6 months) to assess the effect of the group at specific time points.

If Ac RBD as a quantitative variable is available, a GEE regression model with appropriate link function for continuous outcome will be used. Generalized linear models will be used to assess the effect of the group at specific time points (3 months and 6 months).

If there are differences in censoring by group, an additional GEE model will be used with inverse probability of censoring weights (IPCW) to assess the bias potentially induced by attrition during follow-up to 6 months. This method first estimates the probability of dropout to construct IPCWs, and then fits the GEE model with these IPCWs.

24. Secondary outcome analyses

The analysis for N antibodies at three time points between study groups will follow the approach described for RBD antibodies as a dichotomous variable.

For COVID-19 confirmed cases, a chi-squared test of independence will be used to compare the proportion of symptomatic and asymptomatic participants between the study groups. Cox proportional hazard models will be used to compare the risk of a COVID-19 outcome between the study groups, measured at six different time points.

The Ac criteria and B, CD4+ T, and CD8+ T lymphocytes are measured at baseline and 6 months post-vaccination. These criteria will be analyzed on their original log-transformed measurement scales (continuous variables). ANCOVA will be used to compare the groups at 6 months post-vaccination using the baseline measurement as a covariate. The CD4 or CD4/CD8 ratio with Ac-n (log-transformed) will be estimated using Spearman's correlation with a 95% confidence interval.

25. Adverse and Serious adverse events

Adverse events (AE), including serious adverse events (SAE), will be monitored and tracked using a logbook or monthly form asking participant if they had COVID-19 in the last month or any other adverse event self-reported at another moment. They will be coded according to MedRA standards and will be summarized per intervention group.

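### The S3 rule for an asymptomatic COVID-19 case requires neither a negative baseline anti-N nor absence of symptoms, so pre-trial infections and some untested symptomatic cases can be counted as asymptomatic trial cases

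*SAP*

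**What the plan says.** - **Rule (SAP section 20, Secondary outcomes).** A participant is "asymptomatic if the anti-N test confirms that the subject had COVID-19, but the subject never reported a positive COVID-19 test during the time period". The period is not defined, and the visit or visits whose anti-N result counts are not named.
- **Objective (section 8, S3).** The comparison concerns "antigens or PCR confirmed cases of COVID-19 with symptoms and the proportion of COVID-19 asymptomatic cases".
- **Sampling (section 8, S2).** The plan compares the "presence of anti-N antibodies through a longitudinal analysis at three different time points": baseline, 3 months and 6 months. A baseline value therefore exists.
- **Eligibility (section 9).** The exclusion for earlier COVID-19 reads "patients who had COVID-19 in the last 3 months (clinical and/or serological data retrospectively, subgroup of 100 participants only". Outside that subgroup, earlier infection is not an exclusion.
- **Assay (section 20).** Anti-N has "90% sensitivity and 95% specificity".
- **Case finding (sections 12 and 25).** "If a participant reports symptoms related to an infection, we will ask them to realize a COVID-19 test", with rapid tests supplied to those who cannot get tested. There is also a "logbook or monthly form asking participant if they had COVID-19 in the last month".
- **Analysis (section 24).** "For COVID-19 confirmed cases, a chi-squared test of independence will be used to compare the proportion of symptomatic and asymptomatic participants" between the groups. No baseline restriction is added.

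**The concern.** A positive anti-N result shows that an infection occurred at some time; it does not date it. The rule does not use the one measurement that could separate old from new infection, the baseline anti-N. A participant infected well before enrolment, anti-N positive at every visit and never infected on study, meets the definition.

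The rule also puts 'no reported positive test' in place of 'no symptoms'. A symptomatic participant who did not test, tested falsely negative or did not report the result is classed as asymptomatic. Conversely, a participant with a positive test and no symptoms fits neither class, because S3 defines the other class as confirmed cases with symptoms.

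At stake is whether S3 compares trial infections at all. With all participants as denominator, a similar background of old infections and false positives in both arms pulls the risk ratio towards 1. If the test is run among cases only, which section 24 permits as a reading, the same background does not cancel and can create a difference or hide one.

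**Working it through.** **Reading the text.** The rule has two conditions: anti-N positive, and no positive test reported in the period. Neither dates the infection and neither concerns symptoms. Sections 9, 12, 24 and 25 add no condition that would do so. This part needs no arithmetic.

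**Inputs for the size.** The SAP states no expected figure for S3, so there is none to reproduce.
- From the SAP: sensitivity 0.90, specificity 0.95, planned total 688.
- Assumed: b = share infected before the trial, 10-50%; i = new asymptomatic infection among the rest, 10-20%; true risk ratio 0.67; independent assay errors; no waning; no reinfection.

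**All participants as denominator, one follow-up visit.**

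Flagged as written = (1-b)[0.90i + 0.05(1-i)] + 0.90b. Share that are new infections = (1-b)(0.90i) / flagged.

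- b = 0.2, i = 0.10: 0.072 + 0.036 + 0.180 = 0.288, so the share is 0.072/0.288 = 25%. With i = 0.067, flagged = 0.2656, and the apparent ratio is 0.2656/0.288 = 0.92.
- Least favourable, b = 0.5, i = 0.10: 0.045/0.5175 = 9%; ratio 0.5035/0.5175 = 0.97.
- Most favourable, b = 0.1, i = 0.20: 0.162/0.288 = 56%; ratio 0.2375/0.288 = 0.82.

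**Seroconversion from a negative baseline.** The first term is multiplied by 0.95 (uninfected at baseline and correctly negative), the last by 0.10 (earlier infection missed at baseline). For b = 0.2, i = 0.10: 0.0684 + 0.0342 + 0.018 = 0.1206; share 57%; ratio 0.0993/0.1206 = 0.82.

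**If a positive result at either of two visits counts.** False positives rise to 1 - 0.95² = 0.0975. Sensitivity becomes 1 - 0.10² = 0.99 for earlier infection and (0.99 + 0.905)/2 = 0.9475 for new infection, taking half to occur before the 3-month visit. The 0.905 is 1 - 0.95 × 0.10: a false positive at 3 months or detection at 6 months.

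| Rule | New infections among flagged | Apparent ratio (true 0.67) |
|---|---|---|
| As written, one visit | 9-56% | 0.82-0.97 |
| As written, either visit | 8-50% | 0.85-0.98 |
| Seroconversion at 6 months | 39-78% | 0.76-0.88 |
| Seroconversion at 3 or 6 months | 33-68% | 0.80-0.90 |

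**Counts under a different set of assumptions.** Take 688 participants, 30% infected earlier, 10% infected on trial and half of those reporting a positive test.
- As written: trial infections 688 × 0.10 × 0.5 × 0.90 = 31; earlier infections 688 × 0.90 × 0.30 × 0.90 = 167; false positives 688 × 0.90 × 0.70 × 0.05 = 22. About 220 are labelled asymptomatic.
- With a negative baseline required: about 22, 17 and 21, or 59 in all after rounding.

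**Cases only as denominator.** Take b = 0.2 and, in placebo, 10% asymptomatic and 15% symptomatic (all reported) among those not infected earlier.
- Placebo: asymptomatic label 0.8(0.10 × 0.90 + 0.75 × 0.05) + 0.18 = 0.282; symptomatic 0.8 × 0.15 = 0.12; asymptomatic share 0.282/0.402 = 70%.
- Both types cut by a third: 0.2615/(0.2615 + 0.0804) = 76%. The true share is 40% in both arms, so a difference is created.
- Only asymptomatic infection cut: 0.2596/(0.2596 + 0.12) = 68%. The true contrast is 40% v 31%, so a difference is largely hidden.
- With 6-month seroconversion these become 49% v 54% and 49% v 44%.

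The symptom part cannot be sized: the SAP gives no rate of untested symptomatic illness.

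**The case against.** The strongest reply is that the phrase about the time period may be meant to cover the whole classification, so that only infections during follow-up count. Since anti-N is measured at baseline, that intention could be carried out. The SAP does not say this, however, and gives no rule for dating the infection. If it is the intention, stating it is the correction asked for.

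Second, a reported positive test is a reasonable proxy for symptoms when symptoms trigger a test request, rapid tests are supplied and a monthly form asks about COVID-19. This stands in part. It reduces misclassification without removing it, and it makes the symptom part the lesser one.

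Third, the numbers rest on assumptions, and 'no waning' matters most. If earlier infections were detectable at follow-up only 30% of the time (also an assumption), the central case becomes 0.072/(0.072 + 0.036 + 0.060) = 43%, and the ratio 0.1456/0.168 = 0.87. The dilution is smaller but remains.

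Fourth, randomisation balances earlier infection in expectation. That is why no directional bias is claimed when all participants form the denominator; it does not help when cases do.

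Finally, seroconversion barely repairs the equal-effect cases-only example: the false gap falls only from about 6 to 5 points. This is true, and is a reason to settle the denominator as well.

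**Conclusion.** The concern holds. As written, the rule can count pre-trial infections and some untested symptomatic infections as asymptomatic trial cases, and it leaves test-positive participants without symptoms unclassified. These follow from the text and need no assumption.

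The size does need assumptions. Over the prevalences considered, most flagged participants are not new asymptomatic infections except at the favourable end, and the apparent risk ratio lies well towards 1. The ranges are illustrations, not estimates for this trial; waning would reduce the dilution.

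Only S3 is affected. The primary RBD analysis does not use this rule. The point should be fixed, but it does not threaten the trial's main conclusion.

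**What to change.** Amend SAP sections 20 and 24 before unblinding, so that the change cannot appear driven by results:

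1. Define the period as baseline to 6 months.
2. Define a serology-only trial infection as anti-N negative at baseline and positive at 6 months. Use positive at 3 or 6 months as a sensitivity analysis.
3. Report participants who are anti-N positive at baseline separately.
4. Classify all cases, including test-positive ones, as symptomatic or asymptomatic from recorded symptoms where available. Otherwise label serology-only cases 'unreported (serology-only) infection'.
5. State whether the chi-squared test uses all participants or cases only.
6. Add a sensitivity analysis for the stated assay accuracy, because seroconversion does not remove new false positives.

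The cost is wording and programming; no new sample is needed. There are downsides. Serology-only cases can be counted only in baseline-negative participants, so reinfections in the others are lost unless a test was reported. A 6-month-only rule can miss anti-N that has waned since 3 months, while the 3-or-6 rule nearly doubles false positives (5% to 9.75%). The SAP does not show systematic symptom collection over six months, so some cases will stay unclassified.

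### The primary test in SAP section 23 is an unspecified group-by-time interaction, but the objective and the 80% power belong to the 6-month comparison

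*SAP*

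**What the plan says.** Section 8 (Study Objectives) gives the primary objective as: "Reduce the percentage of elderly individuals not presenting RBD antibodies, six months after the booster vaccine dose", probiotic against placebo. The same section lists the longitudinal comparison as secondary: "Obj S1: Compare between study groups the presence of RBD antibodies through a longitudinal analysis at three different time points".

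Section 11 sizes the trial on the 6-month percentage. It assumes an "expected proportion of 30% of elderly individuals not presenting RBD antibodies in the placebo group at 6 months" and aims to "detect a relative difference of 33%, with a two-sided alpha of 5% and a power of 80%; 584 participants are required". Allowing for 15% attrition, the total is 688.

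Section 23 (Primary outcome analyses) specifies a GEE logistic model with group, time (baseline, 3 and 6 months), age group and sex, and then says: "The main parameter of interest in this model will be the interaction between the group and time". The comparison at single visits comes after that, as an addition: "Logistic regressions will also be performed for fixed time strata (3 months and 6 months". Section 21 also plans chi-squared or Fisher tests of RBD detectability between groups.

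**The concern.** Sections 8 and 11 point to one between-group comparison at one visit. Section 23 makes a different quantity primary, and it is the one that section 8 assigns to S1. Two things follow.

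- **Power.** The interaction compares change from baseline between arms. Under randomisation the baseline difference between arms is zero in expectation, so subtracting it leaves the expected effect unchanged but alters the variance. The 80% was calculated without that term.
- **Definition.** With three visits, the interaction could mean the month-6-versus-baseline term, the month-3-versus-baseline term, both jointly (2 df), or a slope if time is linear. The SAP does not choose. A joint test can reject because of a 3-month difference when nothing has happened at 6 months.

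At stake is which result decides the trial, and whether that choice could be made after the results are seen.

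**Working it through.** **1. Reproduce the sample size.** Inputs from section 11: 30% in placebo, 33% relative reduction (20.1%, or 20.0% if one third is meant), two-sided 5%, 80% power. Section 10 gives 1:1 allocation.

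- Pooled variance, 30% vs 20%: n = [1.960·√(2·0.25·0.75) + 0.842·√(0.21+0.16)]² / 0.10² = (1.200+0.512)²/0.01 ≈ 293.2, so 294 per arm, 588 in total.
- Unpooled variance: n = (1.960+0.842)²·0.37/0.01 ≈ 290.4, so 291 per arm, 582 in total.
- With 20.1%: 600 (pooled) or 594 (unpooled).
- Power at 292 per arm, 30% vs 20%: 79.8% (pooled) to 80.2% (unpooled).
- Attrition: 584/0.85 = 687.1, so 688.

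The stated figure is therefore that of a simple two-proportion comparison at 6 months.

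**2. The same effect as an interaction, one case by hand.** Take 292 per arm, 30% vs 20.1% at 6 months, and an assumed baseline rate of 30% in both arms. The variance of a logit in one arm is 1/[n·p(1−p)].

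- Log odds ratio at 6 months: logit(0.30) − logit(0.201) = −0.847 + 1.380 = 0.533.
- 6-month variances: 1/(292·0.21) = 0.01631 and 1/(292·0.1606) = 0.02132, sum 0.03763, SE 0.194. z = 2.75 and power is 78.4%.
- The interaction adds the two baseline variances (2 × 0.01631 = 0.03262) and subtracts 2r·(0.01631 + √(0.02132·0.01631)) = 2r·0.03496, where r is the correlation between the two binary results.
- r = 0: variance 0.07025, SE 0.265, z = 2.01, power 52%.
- r = 0.4: variance 0.04228, SE 0.206, z = 2.59, power 74%.
- r = 0.6: variance 0.02830, SE 0.168, z = 3.17, power 89%.

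Break-even with the direct test is at 0.03262 = 2r·0.03496, so r ≈ 0.47. With a 10% baseline rate the same algebra gives r ≈ 0.71, and power at r = 0, 0.2, 0.4 and 0.6 is 35%, 42%, 52% and 67%.

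**3. Wider grid by simulation.** 6,000 trials per setting, 292 per arm, 30% vs 20% at 6 months, 10% in both arms at 3 months, exchangeable latent normal correlation. Robust Wald tests with saturated group-by-time terms, without age and sex. Baseline rate, 3-month rate and correlation are assumptions. Cells show month-6-versus-baseline power / joint 2-df power, in %.

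| Latent correlation | Baseline 10% | 20% | 30% | 40% |
|---|---|---|---|---|
| 0.3 | 41 / 47 | 54 / 52 | 61 / 56 | 64 / 59 |
| 0.5 | 45 / 51 | 62 / 61 | 70 / 66 | 70 / 66 |
| 0.7 | 52 / 59 | 73 / 71 | 80 / 78 | 81 / 79 |

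The direct 6-month test has 79–81% throughout. An analytic Wald calculation agrees within about 2 points. At latent correlation 0.8 it gives 81–86% for the month-6 term with baseline 20–40%.

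Section 14 reports that "only 9.8% of subjects were lost at some point during the study". If 688 were randomised (an assumption), 688 × 0.902 / 2 ≈ 310 per arm remain. At latent correlation 0.3–0.5, power is then 82–83% (direct), 43–75% (month-6 term) and 48–70% (2 df).

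**4. Effect at 3 months only, none at 6 months.** Baseline 30%, latent correlation 0.3–0.5, the SAP's 33% relative effect applied at 3 months. The joint 2-df test rejects in 21–23% of trials (10% vs 6.7% at 3 months), 32–36% (15% vs 10%), 43–49% (20% vs 13.4%) or 62–69% (30% vs 20.1%). The month-6-versus-baseline term stays at about 5%.

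**The case against.** The best defence is that section 23 lists time as three visits, which suggests a categorical factor. On that reading, with randomised arms, the month-6-versus-baseline term targets in expectation the same odds ratio as the 6-month regression. This is correct. For that contrast the faults are that it is not named and not powered; the question it asks is not wrong. The false-signal argument in step 4 applies only to a joint test, which the SAP neither states nor excludes.

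The size of the power loss is also open to challenge.

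- Latent correlations of 0.3–0.5 correspond to only about 0.17–0.32 between the actual detectable/undetectable results (at 20–30% undetectable), and 0.7 to about 0.45–0.48. Above that, the interaction can beat the direct test.
- The lowest figures need a 10% baseline rate. Participants enter more than five months after their last dose, and the SAP assumes 30% undetectable six months after a dose, so the 30% column may be nearer the truth. That is an inference, not a stated value.
- The 62–69% figure assumes 30% undetectable in placebo at 3 months. At the 10% used in the power grid it is 21–23%.

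These points limit what can be said about size. They do not remove the contradiction between sections 8, 11 and 23, and a 6-month regression that is planned but not designated primary does not resolve it.

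**Conclusion.** The point holds: section 23 is wrong as written. The sample size is sound for the 6-month comparison, but the parameter named as primary is a different one, its contrast is undefined, and it belongs to objective S1. Its power cannot be given as one number. Under low to moderate within-person correlation it falls short of 80%: on the binary scale, the month-6-versus-baseline term stays below 80% at every correlation of 0.4 or less for baseline rates of 10–50%. Under strong correlation with a baseline rate of 20% or more it can exceed 80%. A shortfall is therefore likely but not certain, and depends on inputs the SAP does not give. That the stated 80% was calculated for another test does not depend on those inputs.

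**What to change.** In section 23, name one primary test: the between-group contrast in RBD detectability at 6 months, adjusted for age group and sex, at a two-sided 5% level. State whether it comes from the planned 6-month logistic regression or as the month-6 group contrast from the GEE. Place the group-by-time interaction and the 3-month comparison under objective S1, and state there how time is coded and which interaction contrast is tested. Label the section 21 between-group tests and any quantitative RBD analysis as supportive.

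No new model, data or participants are needed, and the stated 80% then refers to the test that decides the primary objective. Because section 14 shows that follow-up data already exist, enter the change with its reason in the section 5 revision table while allocation is still blinded, and check it against the protocol.
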